PROTOCOL: REPLAMOD

PROMOTER: OSR

TITLE: Histological Modifications of Postmenopausal Vaginal Mucosa After Repeated CO₂ Laser Treatment

Aim of the study: To assess the long-term histological and clinical efficacy of MonaLisa Touch procedure for the management of the Genitourinary Syndrome of Menopause (GSM) in postmenopausal female patients.

Study design: This will be a prospective case series.

Background: The Genitourinary Syndrome of Menopause (GSM), previously known as Vulvovaginal Atrophy (VVA), is a condition seen in postmenopausal estrogen-deficient women. This condition includes both histological and clinical modifications at the genital level which can significantly lower quality of life and lead to female sexual dysfunction, social isolation and depression in this population. Clinically, GSM include symptoms related to the lower urinary tract (dysuria, urgency, frequency, nycturia, urinary incontinence or frequent urinary tract infections) and to the vulva/vagina (dryness, itching, or dyspareunia).¹ Histologically, GSM presents alterations in collagen type I fibrils-to-collagen type III fibrils ratio with loss of their trabecular disposition (collagen fibrils become flattened), it results in decreased quantity of elastic fibers and lubricant secretions, reduced vascularization, and thinning/flattening of the vaginal epithelium.² Postmenopausal women who suffer from GSM can be managed firstly with moisturizers and lubricants and if these fail to control the symptoms they can be treated with pharmacotherapy based on vaginal estrogen preparations.³ Though the effect of local estrogen therapy is often effective, medical adherence among patients is variable (52-74%)⁴ and the use of estrogen is contraindicated in women having history of breast or endometrial cancer, thromboembolism, or coronary artery disease.⁵ Having an effective non-pharmacologic treatment for the management of GSM would therefore be an attractive option for treatment.

MonaLisa Touch CO₂ fractionated laser is a novel, minimally invasive therapy that helps restore vaginal health. The U.S. Food and Drug Administration (FDA) approved the technology for the excision, vaporization, and ablation of tissues and since then it has been used in many different fields of medicine⁶, but it is not approved for the treatment of vulvovaginal atrophy or GSM at the present time. Though observational studies show a possible benefit of MonaLisa Touch in the treatment of vulvovaginal atrophy and GSM^{7,8,9,10}, no studies with long-term follow-up have been performed to date.

We propose a prospective case series of 15 postmenopausal women with bothersome symptoms of GSM treated with MonaLisa Touch CO₂ laser. We hypothesize that even in the long term MonaLisa Touch will significantly improve GSM histologically and clinically from baseline.

Inclusion Criteria:

- Italian speaking and able to give informed consent.
- Menopausal females with absence of menstruation for at least 12 months.
- Presence of GSM symptoms.
- Completion of at least two cycles of three laser treatments sessions in previous years.
- Prolapse stage < II, according to the pelvic organ prolapse quantification (POP-Q) system.
- No pelvic surgery within 6 months prior to treatment.
- Understanding and acceptance to the obligation to return to all scheduled visits and follow-ups.

Exclusion Criteria:

- Inability of give informed consent
- History of vulvovaginal condyloma, vaginal intraepithelial neoplasia (VAIN), vaginal carcinoma, lichen sclerosis, lichen planus.
- History of cancers of the lower genital tract (cervix, uterus, vagina).
- History of pelvic radiotherapy.
- Personal history of genital fistula, a thin recto-vaginal septum as determined by the investigator or personal history of a fourth degree laceration during screening physical exam.
- Any other medical condition that the investigators feel would compromise the study.
- Acute or recurrent urinary tract infection (UTI), or genital infection (e.g. bacterial vaginosis, herpes genitalis, candida).
- Stage III or IV pelvic organ prolapse.
- History of any female sexual disorder.

Power analysis: As this is a prospective case series, no formal power analysis is required.

Efficacy Outcomes:

The **primary outcome objective of the study** is to evaluate the histological modifications of the vaginal mucosa after repeated CO₂ Monalisa Touch laser treatment. We shall evaluate the role of this treatment by calculating the difference in vaginal epithelial thickness between the biopsy obtained before the start of laser treatment and the biopsy obtained after treatment. The latter parameter will be calculated by averaging three measurements 150 micrometers from each other and considering as significant a 20% increase in epithelial thickness compared to baseline. We will then compare the number of papillae, the amount of glycogen present at the epithelial level (by PAS reaction), the ratio between the number of type I collagen fibers ("new" collagen) and type III (old collagen), and the number and size of the vessels present in the subepithelial layer. In addition, the study will analyze the safety of repeated laser treatments verifying the absence of fibrosis formation in the vaginal mucosa.

Secondary objectives of the study will include an evaluation of the clinical effects associated with repeated Monalisa Touch CO₂ laser treatments. Questionnaires to address these secondary objectives will include the following:

- Vaginal Health Index (VHI)¹¹ which will objectively measure the severity of vaginal atrophy
- Visual Analog Scale (VAS) which will subjectively measure the severity of vaginal symptoms
- Female Sexual Function Index (FSFI)¹² questionnaire which will assess female sexual function
- Urinary Distress Inventory-6 (UDI-6) and the International Consultation on Incontinence Questionnaire – Urinary Incontinence (ICIQ-UI) which will evaluate the extent of urinary symptoms
- 5-point Likert¹³ scale to assess the impact of GSM symptoms on quality of life (QoL)

Study Design: All participants will be screened to ensure inclusion/exclusion criteria are met. A biopsy will be taken from each patient one month before the first laser treatment and one month

after the last laser treatment. The MonaLisa treatment will be performed monthly for 3 months. MonaLisa treatment with fractional microablative laser system (SmartXide 2 V 2 LR, MonaLisa Touch, DEKA, Florence, Italy) will be performed to the following energy settings and treatment parameters: dot power 30 W, dwell time 1000us, dot spacing 1000um, smart stack parameter from 1 to 3 and emission mode deka pulse. For subjects with concomitant vulvar symptoms, vulvar treatment will be done with the dot power reduced to 26 W, dwell time 800us, dot spacing 800um, and the smart stack parameter of 1.

During the procedure, an external introducer ring will be inserted into the vaginal canal, the markings on the probe will be aligned with the edge of the ring to measure withdrawal of the probe after a series of pulses will be delivered, and the probe will be rotated of 60°. Laser power could be adjusted before and during the treatment to assure patient comfort. The procedure will be performed in the outpatient clinic, not requiring any specific preparation, analgesia, or anesthesia. Participants will be advised to refrain from engaging in sexual intercourse or bathe for 48 hours after the MonaLisa treatment.

Biopsy samples will be analyzed with Hematoxylin- Eosin and Trichrome staining, PAS reaction for glycogen and immunohistochemistry for CD34, a vessel marker. All clinical questionnaires and VHI will be assessed at baseline and at one month after the last session.

Any medical changes will be reported to the research team who will then evaluate for any impact on the study. Any adverse effects reported by participants will also be recorded and managed accordingly.

Fifteen subjects will be considered for the study. All materials will be kept confidential and maintained by the research coordinator in a locked cabinet.

The participants will keep the research team aware of any changes in medical history, and if any adverse effects are detected.

Data Collection:

- Biopsy baseline visit -Visit 1:
 - Inclusion/Exclusion criteria;

- Collection of patient anamnestic information (age, parity, years since menopause, previous pathologies, previous surgical interventions, BMI, use of estrogenic therapies, sexual activity);
- VAS, FSFI, ICIQ-UI, UDI6 e Likert questionnaires completion;
- Informed Consent signing;
- Bioptic procedure;
- VHI completion from research coordinator;
- Laser treatment visits (three visits at one month interval) - Visit 2, 3, 4
 - Monalisa Touch Laser procedure
 - Adverse events including inability to complete the procedure due to discomfort or constricted vagina.
- Follow-up visit (1 month from the last laser treatment) – Visit 5
 - VAS, FSFI, ICIQ-UI, UDI6 e Likert questionnaires completion;
 - Bioptic procedure;
 - VHI completion from research coordinator;

Data Management: To ensure the protection of each subject's personal health information (PHI), one master Excel file containing subject PHI including name and medical record number will be kept on a password-protected and SharePoint computer. The participant shall be given a unique identification number used for the purpose of de-identified data collection and analysis.

Any hard-copy forms for data collection will be kept in a locked cabinet in the PI's office, which shall be locked at all times, at Urogynecology department at Ospedale San Raffaele Milan, Italy. All forms will contain de-identified information. Identification numbers will correspond to the subjects listed in the master Excel file.

Summary: GSM is a progressive and devastating condition in menopausal women, and is associated with bothersome irritative symptoms compromising the quality of life if this population. MonaLisa Touch laser treatment has shown initial promise in reversing postmenopausal vaginal atrophy, but its efficacy in treating symptoms of GSM long term is lacking. This study is designed

to investigate the long term feasibility of using Mona Lisa laser therapy to treat GSM symptoms in postmenopausal women.

References:

-
- ¹ Cagnacci A, Xholli A, Sclauzero M, et al. Vaginal Atrophy across the Menopausal Age: Results from the ANGEL Study. *Climacteric*. 2019;22(1):85-89.
 - ² Fadare O et al. The Spectrum of Morphologic Alterations Associated With Infarction in Endometrial Polyps: A Report of 41 Cases. *Int J Gynecol Pathol*. 2017.
 - ³ The North American Menopause Society. Management of Symptomatic Vulvovaginal Atrophy: 2013 Position Statement of The North American Menopause Society. *Menopause*. 2013;20:888-902.
 - ⁴ Shulman LP, Portman DJ, Lee WC, et al. A Retrospective Managed Care Claims Data Analysis of Medication Adherence to Vaginal Estrogen Therapy: Implications for Clinical Practice. *Journal of Women's Health* (2002) 2008;17:569-78.
 - ⁵ Faubion SS, Sood R, Kapoor E. Genitourinary Syndrome of Menopause: Management Strategies for the Clinician. *Mayo Clin Proc*. 2017;92(12):1842-1849.

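### The aim and hypothesis claim long-term efficacy, but the only post-treatment assessment is one month after a further cycle in women already treated

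*Protocol*

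**What the plan says.** Four places in the protocol set the claim:

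- **Aim of the study:** "To assess the long-term histological and clinical efficacy of MonaLisa Touch procedure for the management of the Genitourinary Syndrome of Menopause".
- **Background, rationale:** observational studies suggest benefit, but "no studies with long-term follow-up have been performed to date".
- **Background, hypothesis:** "We hypothesize that even in the long term MonaLisa Touch will significantly improve GSM histologically and clinically from baseline".
- **Summary:** it repeats that long-term evidence on symptoms is missing, and describes the study as one of long-term feasibility.

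No section defines long-term.

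The population and schedule are set elsewhere:

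- **Inclusion Criteria:** "Completion of at least two cycles of three laser treatments sessions in previous years". GSM symptoms must also be present at entry.
- **Study Design (schedule):** biopsies are taken one month before the first session and one month after the last, with monthly sessions for three months. For the clinical measures, "All clinical questionnaires and VHI will be assessed at baseline and at one month after the last session".
- **Data Collection:** Visit 1 is baseline, Visits 2 to 4 are the laser sessions, and Visit 5, one month after the last session, is the final visit.

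The Efficacy Outcomes section is worded differently from the aim. The primary objective is "to evaluate the histological modifications of the vaginal mucosa after repeated" laser treatment, and the secondary objectives also refer to repeated treatment. Neither uses the term long-term.

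**The concern.** The aim, the hypothesis and the stated evidence gap all lead a reader to expect information on how long an effect lasts. The schedule has a single post-treatment assessment, at one month, so persistence beyond that point is never observed. Baseline also follows earlier laser cycles, so the change from baseline does not capture the total effect of treatment over the years either.

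What is at stake is the conclusion. If Visit 5 is better than Visit 1, the protocol as written invites the report that the laser is effective in the long term and that a gap in follow-up has been filled. Readers could take this as evidence of durability from a study that contains none.

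**Working it through.** The protocol gives no figure to reproduce. The check sets its schedule against its claim.

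**Timeline, with month 0 as the first study session** (from Study Design and Data Collection)

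| Visit | Month | Content |
|---|---|---|
| 1 | -1 | biopsy, VHI, questionnaires |
| 2, 3, 4 | 0, 1, 2 | laser session, adverse events |
| 5 | 3 | biopsy, VHI, questionnaires |

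- Last session to last assessment: 3 - 2 = 1 month.
- First study session to last assessment: 3 - 0 = 3 months.
- Baseline biopsy to final biopsy: 3 - (-1) = 4 months.
- Post-treatment efficacy assessments: 1. Assessments after Visit 5: 0.

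**Exposure** (from Inclusion Criteria and Study Design)

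- Sessions before Visit 1: at least 2 x 3 = 6.
- Sessions by Visit 5, for a woman who completes treatment: at least 6 + 3 = 9.
- Share of sessions falling between the two biopsies: at most 3/9 = 33%.

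The baseline biopsy is taken at Visit 1, where eligibility, including the earlier cycles, is checked. The first laser treatment that it precedes is therefore the first session of the study cycle, not the first the woman ever had.

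**What each reading of long-term would need**

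1. *Persistence after treatment stops.* This needs assessments well after the last session, and there are none beyond one month. Visit 1 cannot serve as a late follow-up of the earlier cycles: the interval since them is unspecified, no value from before them is used, and entry requires current symptoms.
2. *Cumulative effect over several cycles.* This needs a value from before the first cycle. None is collected or used.
3. *Continued response in women treated over years.* Visit 1 against Visit 5 addresses this, as the one-month response to a further cycle. It fits the word repeated in the title and objectives, but not a rationale based on missing long-term follow-up.

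The biopsy timing, the clinical assessment timing and the visit list agree with one another, so the schedule is not in doubt. A separate SAP could not add observations that the protocol does not schedule.

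**The case against.** The strongest defence is the third reading: long-term means long-term use. The title and objectives speak of repeated treatment, entry requires earlier cycles, and the hypothesis can be read as asking whether a further cycle still helps after several. On that reading the before-after comparison is the right one, and the safety objective of "verifying the absence of fibrosis formation in the vaginal mucosa" is informative after at least three cycles. No objective promises a comparison with a never-treated state, so the session counts add little to the argument. The one-month follow-up is stated openly, and the expected harm lies in later reporting.

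Much of this stands. The repeat-cycle question is testable and matches the title and objectives, no endpoint or visit is mis-specified, and the figure that matters is the single month of follow-up. A descriptive statement on fibrosis after at least three cycles also remains possible.

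The defence does not rescue the wording. The rationale is about missing long-term follow-up, and the Summary says that long-term efficacy on symptoms is unproven. Both point to duration of effect, which a one-month assessment cannot address. If the sponsor means repeated use, the text has to say so, and the follow-up gap can no longer be the justification.

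**Conclusion.** The concern holds and should be fixed. The protocol claims long-term efficacy, but its design yields one post-treatment efficacy assessment, 1 month after the last session, in symptomatic women with at least 6 earlier sessions. The supportable conclusion is the change one month after a further three-session cycle in such women. Durability beyond one month and cumulative effect against a never-treated state are not observed.

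The defect lies in the stated claim, not in the endpoint, schedule or comparison. The conclusion rests only on the protocol's own visit schedule and entry criteria. It needs no numerical threshold for long-term: no part of the protocol supports applying the term to one assessment at one month.

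**What to change.** Reword four places and add one sentence:

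- **Aim and hypothesis:** replace the long-term wording with efficacy one month after a further three-session cycle in women previously treated with at least two cycles.
- **Background, rationale:** say that the study addresses response to a repeat cycle and does not fill the gap in long-term follow-up.
- **Summary:** make the same change to the restated gap, and replace long-term feasibility with the same scope.
- **Limitation sentence:** durability beyond one month, and cumulative effect against a never-treated state, are not assessed.

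The fibrosis objective can stay as a descriptive statement after at least three cycles.

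These edits change no visit, procedure, endpoint or analysis. The cost is a less ambitious claim, and the study must rest its justification on the repeat-cycle question, because long-term evidence is the only gap it now cites. The alternative is to keep the long-term aim and add later assessments. That would answer the durability question, but it means extra visits and biopsies and is not cheap.

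### The long-term efficacy claim does not fit a sample limited to women symptomatic after at least two earlier laser cycles; the design can show only short-term change over one further cycle

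*Protocol*

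**What the plan says.** Only the protocol is at hand. Its opening aim is "To assess the long-term histological and clinical efficacy of MonaLisa Touch procedure", and the Background ends with "We hypothesize that even in the long term MonaLisa Touch will significantly improve GSM histologically and clinically from baseline". The Summary repeats the long-term purpose.

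The Inclusion Criteria require "Presence of GSM symptoms", with no severity threshold and no restriction on symptom type. They also require "Completion of at least two cycles of three laser treatments sessions in previous years", with no upper limit on cycles and no interval since the last one. No criterion concerns response to those cycles.

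The primary objective "is to evaluate the histological modifications of the vaginal mucosa after repeated CO₂ Monalisa Touch laser treatment". It is assessed by "calculating the difference in vaginal epithelial thickness between the biopsy obtained before the start of laser treatment and the biopsy obtained after treatment", and the Efficacy Outcomes text adds "considering as significant a 20% increase in epithelial thickness compared to baseline".

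On timing, the Study Design text states "A biopsy will be taken from each patient one month before the first laser treatment and one month" after the last one, with three monthly sessions in between. Data Collection places the first biopsy at Visit 1 and the second at Visit 5. The Visit 1 history covers demographic, obstetric, menopausal, medical, surgical, hormonal and sexual items. It does not list the number of earlier laser cycles, their dates or their effect. There is one group of 15 women and no comparator.

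**The concern.** A claim of long-term clinical efficacy rests largely on women who were treated and stayed well. Here a woman who is wholly symptom-free after her earlier cycles is ineligible. Those who enter are women the earlier cycles did not help enough and women who were helped and then relapsed. The two kinds are not told apart in the listed data.

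Two things are at stake. First, a favourable result could be reported as evidence of lasting benefit, which neither the sample nor the visit schedule can supply. Second, a weak result would be ambiguous: it could mean that a further cycle does little, or that many participants were earlier non-responders. A statistical analysis plan could not repair this later, because eligibility and the Visit 1 items are set in the protocol.

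**Working it through.** The protocol gives no alpha, power, standard deviation or dropout, and states that no formal power analysis is needed, so there is no sample-size figure to reproduce. The check is mainly one of logic, with illustrations on assumed inputs.

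**1. Who can enter.** At least two cycles of three sessions gives 2 × 3 = 6 or more earlier sessions. Adding the symptom criterion leaves:

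| State after the earlier cycles | Eligible on these two criteria? | Identifiable from the listed Visit 1 items? |
|---|---|---|
| Complete, lasting symptom relief | No | Not enrolled |
| Partial lasting relief, residual symptoms | Yes | No |
| Relief, then relapse | Yes | No |
| Never relieved | Yes | No |

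**2. What the contrast spans.** The start of treatment in the primary contrast can only mean the start of the on-study cycle. Visit 1 is where eligibility is checked, consent signed and the first biopsy taken, and by then the earlier cycles are complete. The interval between biopsies is about 1 month (biopsy to first session) + 2 months (first to third session) + 1 month (third session to follow-up) = 4 months. No value from before the first-ever cycle is used, and nothing is measured beyond one month after the last session. Both facts block a reading of durability, independently of the symptom criterion.

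**3. How the mix could matter for the 20% mark.** Assume relapsers gain D and earlier non-responders gain 0, with a share p of relapsers. The mean change is p × D. With D = 30%:
- p = 0.9: 27%
- p = 0.6: 18%
- p = 0.3: 9%

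The mean reaches 20% at p = 20/30, about two-thirds. The values of p and D, and the zero gain in non-responders, are all assumptions. So is carrying symptomatic non-response over to epithelial thickness.

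**4. What 15 women can and cannot resolve.** The 95% confidence interval half-width for the mean paired change is t(0.975; 14)/√15 = 0.55 SD of the change, so the pooled mean can be estimated. For a difference between two earlier-response groups it is t(0.975; 13) × √(1/n₁ + 1/n₂):
- 7 and 8 women: 1.12 SD
- 5 and 10 women: 1.18 SD
- 3 and 12 women: 1.39 SD

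No useful comparison between the groups is possible, even if earlier response is recorded.

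**5. Direction of the selection.** Selecting on present symptoms also invites regression to the mean. For a symptom score with retest correlation r and an entry cut at c SD, the expected apparent improvement without any treatment effect is (1 − r) × φ(c)/(1 − Φ(c)). For r from 0.9 down to 0.5 and c from −0.5 to +0.5, this runs from 0.05 to 0.57 SD (r and c assumed). It favours the laser on symptom scores, whereas excluding women with lasting relief and admitting non-responders works the other way. The net direction is unknown.

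**The case against.** Enrolling symptomatic women in a study that treats and biopsies everyone is an ordinary choice, and the two criteria do not contradict each other. The within-woman change is a coherent estimate for a coherent population and is close to the primary objective. Averaging over better and worse responders does not make a mean unreadable, and what limits attribution to the laser is chiefly the lack of a control. The failure to show durability also comes from the late baseline and the short follow-up, and dropping the symptom criterion would leave both in place. All of this stands.

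A reader might go further and infer that every woman whose benefit lasted is excluded. The text does not support that. With no severity threshold, partial lasting relief qualifies. The Background counts urinary symptoms as part of the syndrome, so a woman with lasting vaginal relief and urinary complaints qualifies. No criterion selects on epithelial thickness, so lasting histological benefit is not excluded at all. The Background does describe the intended sample as women troubled by their symptoms, which narrows the room for substantial lasting relief but does not close it.

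The objection does not remove the mismatch. The aim and hypothesis still claim long-term efficacy for a sample that omits complete, lasting symptom relief and is followed for one month after treatment. Longer follow-up alone would test durability only in women whose earlier relief was absent, incomplete or lost.

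**Conclusion.** The point holds as a mismatch between claim and design. The study cannot show durability of benefit, for three reasons together: complete lasting symptom relief is ineligible, the baseline follows the earlier cycles, and follow-up ends one month after the last session. It can estimate the average short-term, uncontrolled change over one further cycle in women symptomatic after at least two, and it cannot interpret that change by earlier response.

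The durability conclusion rests on the protocol text alone. The size of any effect of the mix is unknown: the range of 9% to 27% is an illustration on assumed inputs. Two stronger inferences are not supported. One is that the effect of re-treatment cannot be read at all; the average change can be estimated, though without a control it cannot be firmly attributed to the laser. The other is that the selection works only against the laser; regression to the mean can work in its favour. The matter should be corrected but does not stop the study.

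**What to change.** - **Wording.** Recast the aim, hypothesis and Summary as *short-term histological and clinical change over a further cycle in women whose GSM symptoms persisted or returned after at least two earlier cycles*, and drop the long-term efficacy claim.
- **Visit 1.** Record the number of earlier cycles, the time since the last one, and whether and for how long each relieved symptoms, from the clinic record where possible.
- **Reporting.** List individual histological and clinical changes by earlier response, descriptively, with no subgroup inference in 15 women.
- **Screening log.** Count previously treated women screened out because they were symptom-free. This is a snapshot without duration or histology, and it does not measure durability.

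The cost is a wording change, a few Visit 1 items and one log line. Treatment, visits and sample size are unchanged. The drawbacks are that recalled response is imprecise and that the stated conclusion becomes narrower.

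### The primary thickness reading has no fixed starting place and no masking of the reader to visit, so the single-arm before/after change is open to placement bias of unknown size

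*Protocol*

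**What the plan says.** The Protocol's section on Efficacy Outcomes makes the primary measure a paired change, obtained by "calculating the difference in vaginal epithelial thickness between the biopsy obtained before the start of laser treatment and the biopsy obtained after treatment". Thickness is found by "averaging three measurements 150 micrometers from each other", and the success mark is set by "considering as significant a 20% increase in epithelial thickness compared to baseline". The text does not say whether that mark applies to each woman or to the group mean.

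The number of readings and their spacing are fixed. No starting point, landmark or random start is given. The later Study Design section lists the laboratory methods ("Biopsy samples will be analyzed with Hematoxylin- Eosin and Trichrome staining", then PAS and CD34) but names no reader and no masking to visit. The closest text is in Data Management, where each woman receives a "unique identification number used for the purpose of de-identified data collection and analysis". That protects her identity. It does not hide whether a slide comes from Visit 1 or Visit 5.

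The study is a case series of 15 women without a control arm. Its stated hypothesis, at the end of the Background, is that "MonaLisa Touch will significantly improve GSM histologically and clinically from baseline".

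**The concern.** Epithelial thickness varies along a section, so the place chosen for three closely spaced readings affects their mean. If the reader is free to choose and knows which slide is post-treatment, the choice can drift towards a thicker stretch after treatment, even unintentionally. Three features make this matter here:

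- The affected value is the primary endpoint.
- No control arm would share the reader effect and so reveal or cancel it.
- More women would not average out a systematic shift, and no statistical adjustment of the recorded values could identify it.

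How the primary measurement is taken is a procedural matter for the protocol. It is not something usually left to a statistical analysis plan.

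**Working it through.** **No planned figure to reproduce.** The Protocol gives no SD, alpha, power or sample-size calculation. The check is a search of the text, followed by an illustration.

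**Text.** Number of readings: stated (three). Spacing: stated (150 micrometers). Start: not stated. Reader: not named. Masking to visit: not stated. Site of the biopsy in the vagina: not stated.

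**Geometry.** If the three readings lie in line on one section, which is the natural reading but is not stated, they span 2 × 150 = 300 micrometers.

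**Illustration: inputs.** From the Protocol: three readings, 150-micrometer spacing, 15 women, 20% mark. Assumed, because the Protocol gives none of them:
- no true change, and normally distributed readings
- within-biopsy CV 10, 15 or 20%
- correlation between readings = rho^(distance/150 micrometers), with rho 0 to 0.9
- three candidate places per section, with the thickest always taken after treatment and an arbitrary one at baseline

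**Formula.** The SD of a three-reading mean is CV × √[(3 + 4·rho + 2·rho²)/9]. The expected largest of three independent standard normal values is 3/(2√π) = 0.846. The apparent rise is therefore about 0.846 × SD, and less where the candidate places are correlated.

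- CV 10%, rho 0: SD = 10% × √(3/9) = 5.77%. Rise = 0.846 × 5.77% = 4.9%.
- CV 20%, rho 0.7: SD = 20% × √[(3 + 2.8 + 0.98)/9] = 17.4%. Rise = 0.846 × 17.4% = 14.7% if the places were independent. Simulation, which keeps the remaining correlation at 1000-micrometer spacing, gives 14.0%.

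**Simulated ranges over the grid (thickest of three).**

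| Candidate places start | Apparent rise in mean thickness | Extra women of 15 at or above 20%, if the rule is per woman |
|---|---|---|
| 150 micrometers apart (overlapping) | 1.9-6.6% | 0.2-1.2 |
| 450-1000 micrometers apart | 4.1-14.0% | 0.3-2.6 |

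The extra women are counted against neutral placement at the same CV, rho and spacing. With neutral placement, the chance that a woman reads at least 20% up is 1.3-25.2%, that is 0.2-3.8 of 15 from noise alone.

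**Milder readers (places 450-1000 micrometers apart).** Taking the thickest of two gives 2.4-9.1%. Taking the thickest of three in only half of the women gives 0.5 × 4.1% = 2.1% to 0.5 × 14.0% = 7.0%.

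**Sensitivity.** Candidate spacing alone moves the result about twofold. Places starting 1000 micrometers apart need 2 × 1000 + 300 = 2300 micrometers of usable epithelium, and the Protocol gives no section length. A separate lognormal model with starts 150 micrometers apart gives about 2.5-3% at CV 10% and 5-6% at CV 20%, in line with the first row. Outside the assumed range the effect grows: with CV 30% and five starts, that model gives a rise in mean thickness of up to about 16%. With a fixed start, both models give no bias in mean thickness.

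**Delay from paired reading.** Visit 1 to Visit 5 = 1 month to the first laser session + 2 months across three monthly sessions + 1 month to the second biopsy = 4 months.

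**The case against.** The strongest reply is that the concern rests on silence. The Protocol does not say that the reader knows the visit or picks the place. A laboratory procedure could settle both, although the Protocol refers to none. This stands as a limit: the document leaves the door open but does not show that bias will occur. A reader might infer that the slides will be read unmasked at a freely chosen spot, and the text does not establish that. Nor does the absence of masking contradict anything else in the Protocol.

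A second reply concerns size. A reader might infer that placement alone could deliver the 20% result. On a group-mean reading of the threshold, the expected rise stays below 20% throughout the assumed grid. Counts of women need a per-woman reading that the Protocol does not state. The upper figures also depend on widely spaced candidate places, and 4.1% is not a floor, because closer places give about 2%. All of this stands.

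Third, noise is the larger problem in these same figures: up to 3.8 of 15 women cross 20% with neutral placement, against at most 2.6 added by the reader. That is correct, and the fix does not reduce that noise or the variation between biopsy sites. But noise alone does not shift mean thickness in one direction, whereas placement can.

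Fourth, the harm is not irreversible. If the slides are kept, they can be recoded and re-read masked. That also stands, and it tempers the urgency.

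**Conclusion.** The point holds in a limited form. The reading rule for the primary endpoint is incomplete, because number and spacing are fixed but the start is not, and no masking to visit is provided. In a single-arm before/after study with a declared expectation of improvement, this leaves the primary change open to placement bias of unknown size.

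The illustration (about 2-7% or 4-14% apparent rise, depending on how far apart the candidate places lie) describes a reader who always favours the thick stretch after treatment. It is not an expected bias. It rests on assumed CV, correlation, spacing, number of places and reader behaviour. The figure of about 0.2-2.6 extra women of 15 needs the further assumption that the 20% rule is applied woman by woman. The documents do not support the claim that the result will be biased, or that placement by itself explains a 20% group rise. The sponsor should make the change because it is cheap and concerns the primary endpoint.

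**What to change.** Add two statements to the Protocol, in Efficacy Outcomes and in the histology paragraph of Study Design:

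1. The intended reader reads the Visit 1 and Visit 5 slides coded to visit and in random order, with the code list held by someone else. Each woman's pair can be read after her own Visit 5, or all pairs in one batch.
2. The reading positions are set by the same pre-specified rule at both visits. A pre-set start with the 150-micrometer spacing kept is enough. This also protects the reading if treated tissue looks different and the masking is imperfect.

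**Cost.** A code list and a little more reading time on 15 × 2 = 30 planned biopsies. No extra biopsy or stain is needed, and no extra reader if the intended one can be kept from the code list. Baseline thickness is read about 4 months later, or longer if all pairs are batched. The safety reading, "verifying the absence of fibrosis formation in the vaginal mucosa", can stay outside the coding so that it is not delayed.

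**What it does not do.** It does not reduce variation between biopsy sites or the chance of a 20% rise from noise. Masked reading of papillae, glycogen, collagen and vessels is an optional extension.
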